We previously conducted a cross-sectional assessment of vitamin D status, intakes and compliance to supplementation in a cohort of children with SCD (n=116), representative of the population of SCD patients followed up at Sainte-Justine UHC (total population is 307)². We measured 25OHD levels in summer and fall in order to capture, not only the contribution of dietary and supplemental vitamin D to vitamin D status, but also of sun exposure. With this approach, we portrayed more accurately the highest vitamin D status these individuals managed to get to. Nevertheless, despite a significant time spent outdoors in summer (108±58 min/day), two-third of children (66%) had suboptimal vitamin D status (<50 nmol/L) while 33% were deficient (<30 nmol/L), thereby confirming that vitamin D synthesis through sun exposure is limited in these children in our latitude during summer. The situation was even worse in fall whereby 77% and 55% of children were vitamin D insufficient (<50 nmol/L) and deficient (<30 nmol/L) respectively. Regardless of season, only 6% of children had vitamin D sufficiency (≥75 nmol/L) with a maximum value of 99 nmol/L. Serum 25OHD levels did not vary according to genotypes (the most severe SS: 41.0±20.4 nmol/L; SC: 45.7±17.9 nmol/L; and β-thal: 40.4±15.9 nmol/L; p=0.767). Vitamin D intakes (353±234 IU) were below recommendations (600IU/day) in 72% of children and came mostly from foods (292±128 IU). Moreover, our data revealed that only 8 children (out of 46 questioned; 17%) took vitamin D supplement and only 50% of these children (n=4 out of 8) reported taking it at least 4 days a week. The high proportion of SCD children with impaired vitamin D status combined to the low proportion of subjects consuming supplements, their poor compliance, their northern geographical location and their limited ability to produce vitamin D from sunlight led us to propose an intervention strategy to overcome these issues.

Vitamin D is important for SCD children

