
RATIONALE

The rationale for the proposed trial is summarized below:

1. **More than two-third** of SCD children followed up at Sainte-Justine UHC are either vitamin D deficient or insufficient during summer and fall and may therefore clinically benefit from improving their vitamin D status.
2. Given the low dietary and supplemental intakes of vitamin D of SCD children, their poor compliance to vitamin D supplementation, their compromised cutaneous synthesis of vitamin D, the presence of other potential contributing factors (e.g. impaired vitamin D metabolism, increased

nutritional demands, lactose intolerance) and the poor adherence to the CanHaem clinical practice guidelines¹⁴ regarding vitamin D, a vitamin D nutritional intervention is clinically and ethically desirable.

3. The fact that conditions associated with vitamin D deficiency/insufficiency are similar to SCD-related complications suggests that correcting vitamin D nutrition of these children may potentially result in clinical improvements and ultimately a better quality of life.

4. Very few SCD children in our cohort had serum 25OHD levels > 75 nmol/L (i.e. 6%), the suggested target level for the extra-skeletal effects of vitamin D. Given that some clinical benefits have been demonstrated in SCD children when serum 25OHD exceeds 75 nmol/L, an effective intervention strategy aimed at normalizing vitamin D status while ensuring reasonable compliance is warranted.

HYPOTHESIS

We hypothesize that administration of a single oral bolus of 300,000 IU of vitamin D₃ to children with SCD represents a safe, acceptable and clinically feasible regimen that will result in the attainment of vitamin D sufficiency (25OHD levels >75 nmol/L) in 80% of participants and in mild improvements in some clinical outcome measures after 3 months.

RESEARCH OBJECTIVES

Primary objectives:

- To assess the feasibility of recruitment and intervention (vitamin D₃ bolus)
- To assess the acceptability of the intervention by patients and parents
- To assess the safety of the vitamin D₃ bolus (serum and urinary calcium levels, serum 25OHD)

Secondary objectives:

- To observe the mean change in total serum 25OHD from baseline to 3 months. At 3 months, a raise of the 25OHD level to 75nmol/L or more is expected.

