Randomisation and allocation concealment: Using a computer-generated random list, children will be randomly allocated to placebo or intervention, using random permuted blocks. The Applied Clinical Research Unit of Sainte-Justine UHC will generate the randomisation scheme. Group allocation codes will be held in a secure location with a restricted access by the Central pharmacy (Sainte-Justine UHC). All participants and research personnel, including the nurse, research trainee and research team will be blinded to group assignment.

Interventions: Experimental group: a single liquid bolus of 300,000 IU oral vitamin D₃, which corresponds roughly to 3,333 IU/day; Control group: placebo identical in taste and appearance. The proposed dose of bolus vitamin D₃ is based upon a previous report showing that 4,000 to 7,000 IU/day administered to SCD children over 12 weeks was effective to correct vitamin D insufficiency in more than 95% of their cohort and led to some clinical improvements¹¹.

Co-interventions: In addition, all subjects will be provided with a 3-month prescription of vitamin D₃ tablets (1,000 IU/tablet) to comply with the CanHaem guidelines¹⁴ and instructed to take 1 pill per day. The research trainee will assess calcium intake and if deemed too low, participants will also receive a prescription for calcium supplements in order to ensure adequate daily calcium intake. The reason for such a co-intervention is to prevent symptoms of hypocalcemia in those who take supplemental vitamin D but have a low calcium intake.

Overall, participants in the experimental group will be taking 4,333 IU/day + dietary vitamin D intake, which falls within the range of 4000 to 7000 IU/day previously found to correct suboptimal status of SCD children¹¹. Placebo group will be taking 1,000IU/day in addition to dietary vitamin D intake. Previously, the evaluation of dietary vitamin D intakes of a sample of children attending the SCD clinic at UHC Sainte-Justine (n = 46) revealed that the children took, on average, 292 +/- 128 IU of vitamin D per day². Therefore, by taking into account dietary vitamin D intakes similar to what we have previously found, the participants in the experimental group will take 4, 625 IU of vitamin D per day in total (supplement + dietary intakes) while participants in the placebo group will take 1, 292 IU per day.

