Observation period duration: The duration of the observation period will be of 3 months +/- 2 weeks, which corresponds to the time between the first appointment at the clinic during which the participants will take the vitamin D bolus and the second appointment. Because this study is a project which is realised in the context of a master's degree, we chose this duration for the observation period so the data could be collected in the proposed sample of patients in the time that we have for that type of study. Although 3 months is a short duration to obtain meaningful clinical improvements, the primary objectives of this study are to evaluate the feasibility, the acceptability and the security of the proposed intervention.

Supplement preparation: The supplier Euro-Pharm will provide the placebo and vitamin D₃ preparations (50,000 IU/mL) in coded bottles. Pharmacy will obtain the allocated treatment through a web-based randomisation system and will prepare the 6-mL bolus in coded syringes.

Supplement administration: Upon randomisation, the research nurse will administer the syringe to the participants and provide the prescription for the daily dose. Participants will be requested to return pillboxes at the end of the study period, coinciding with their next follow-up visit to the clinic (i.e. 3 months +/- 2 week-window).

Compliance assessment: Compliance of bolus retention will be visually assessed by the nurse while compliance to daily regimen will be assessed through pill counts. To maximize compliance, the research trainee will make weekly phone calls in order to gather information on compliance to daily regimen. In addition, pharmacies will be contacted to check if the prescription has been filled.

Sample size: Based on our preliminary data, only 6% of SCD children had vitamin D sufficiency ($\geq 75\text{nmol/L}$). One of our objectives is to bring this proportion to 80%. To detect such an increase with a power of 0.90 and a $\alpha=0.05$ by 2-tailed testing, we need 30 patients per group. Taking into account an attrition rate of 20%, we aim to recruit a total of 72 participants (36 per group).

Outcomes:

1. *Feasibility and acceptability:* Information pertaining to: i) identification and number needed to screen to identify eligible candidates; ii) willingness of patients and parents to participate in the study and of clinicians to recruit; iii) reasons and rates of refusal, recruitment and attrition, and burden of

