Feasibility: Preliminary data showed that we already have access to a large cohort of patients (n=307) through our ongoing collaboration with two SCD expert haematologists. Infrastructure is already in place since we have previously performed data collection in more than a third of the SCD population (n=116) followed up at the clinic. Study is not invasive as those children have their blood drawn at each follow-up visits. Although a certain level of involvement is required from participants and their parents, we believe that a nutritional intervention will be perceived as more acceptable than a pharmacological treatment. For all these reasons, we anticipate few recruitment issues. Supplements (both boluses (placebo and vitamin D₃) will be provided by Euro-pharm at no cost for the study. Ethics approval will be sought and a no-objection letter will be requested from Health Canada, pending results of this review. The no-objection letter is required given that the proposed total amount of vitamin D₃ exceeds the upper intake level (UL) of vitamin D recommended for otherwise healthy children aged 4-8 years (i.e. 3,000 IU) and 9 and older (i.e. 4,000 IU).

[figure not shown]

Fig.1 Experimental design

STATISTICAL ANALYSIS

The analyses will be made using the intention-to-treat model where all subjects are included regardless of their adherence to the study protocol. Differences in outcomes between experimental groups at baseline and endpoint will be assessed using parametric Student's t test or non-parametric

Mann Whitney U test for continuous variables and Chi-square test or Fisher's exact test for categorical variables. Intragroup differences will be assessed using paired Student's t test with Bonferroni adjustment. Analyses will be performed under allocation concealment with unblinding occurring after trial completion and analysis of primary outcomes. Given the pilot nature of our study, subanalyses will be undertaken on variables that may potentially influence the response to vitamin D such as genotype, season of the year or baseline vitamin D status. However, these analyses remain exploratory.

CLINICAL SIGNIFICANCE

By implementing this pragmatic and highly acceptable intervention and achieving a compliance of 100% with the administration of the vitamin D bolus, we expect to: 1) correct vitamin D insufficiency in SCD children; 2) avoid monitoring their 25OHD levels on a regular basis; and 3) ultimately demonstrate improvements in clinical outcomes.

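### The stated inputs (6% vs 80%, power 0.90, two-sided 0.05) need about 8 to 10 children per group, not 30, and 36 per group does not leave 30 after 20% attrition

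*Protocol*

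**What the plan says.** The Sample size paragraph (Protocol, Methodology) starts from preliminary data in which "only 6% of SCD children had vitamin D sufficiency" and sets a target of 80%. For power 0.90 and alpha 0.05 it states that "by 2-tailed testing, we need 30 patients per group". It continues: "Taking into account an attrition rate of 20%, we aim to recruit a total of 72 participants (36 per group"). The 80% target matches the Hypothesis section, which expects that the bolus "will result in the attainment of vitamin D sufficiency (25OHD levels >75 nmol/L) in 80% of participants".

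For between-group comparisons, the Statistical analysis section names the "Chi-square test or Fisher's exact test for categorical variables".

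Two other places bear on the 6%. The preliminary-data section reports that "only 8 children (out of 46 questioned; 17%) took vitamin D supplement". Under Co-interventions, both arms receive a daily tablet: "Placebo group will be taking 1,000IU/day in addition to dietary vitamin D intake".

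**The concern.** A difference of 74 percentage points is very large, and 30 per group looks far too many to detect it with 90% power. This is the protocol's only power statement and its only stated basis for N. If the figure cannot be rebuilt from its inputs, a reader cannot tell which comparison, test or control rate it was meant for.

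The 6% is also a prevalence in children who mostly took no supplement. It is not shown to be the rate expected at 3 months in placebo children prescribed 1,000 IU/day. The real power depends on that placebo rate, which the protocol does not give.

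**Working it through.** **Inputs.** p1 = 0.06, p2 = 0.80, power 0.90, two-sided alpha 0.05, 1:1 allocation, 20% attrition (all from Sample size). Test: chi-square or Fisher's exact (Statistical analysis). z values: 1.960 and 1.2816. Difference d = 0.74, so d² = 0.5476.

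**Attempt to reproduce 30**

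1. *Pooled chi-square formula*, n = [1.960·√(2·p̄·(1 − p̄)) + 1.2816·√(p1(1 − p1) + p2(1 − p2))]² / d², with p̄ = (0.06 + 0.80)/2 = 0.43.
   - 2 × 0.43 × 0.57 = 0.4902, root 0.7001
   - 0.0564 + 0.1600 = 0.2164, root 0.4652
   - n = (1.372 + 0.596)² / 0.5476 = 7.08, so **8**
2. *Continuity-corrected*, n' = (n/4)·[1 + √(1 + 4/(n·d))]² with n = 7.08: 9.59, so **10**.
3. *Fisher's exact test*, power by full enumeration: 0.860 at 8 per group and 0.905 at 9, so **9**.
4. *Uncorrected chi-square*, by full enumeration: 0.907 at 7 and 0.957 at 8. On an exact basis 7 would already do.

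Other readings do not reach 30 either:

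| Reading | n |
|---|---|
| Unpooled variance | 4.15, so 5 |
| Arcsine | 7.11, so 8 |
| Exact one-sample test against 6% | 4 (power 0.973; 0.896 at 3) |
| Exact McNemar, no child loses sufficiency | 10 (0.910; 0.815 at 9) |
| Exact McNemar, 6% lose sufficiency | 14 (0.909; 0.880 at 13) |
| Pooled / continuity-corrected, power raised to 0.99 | 12 / 14 |

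For 6% vs 80% at 29 or 30 per group, exact power exceeds 0.9999 with either named test.

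**Attrition**

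- 30 × 1.2 = 36, the protocol's figure.
- 36 × 0.80 = 28.8, which is below 30.
- 30 / 0.80 = 37.5, so 38 per group (76 in total).
- 36 leaves 30 only if attrition is at most 1 − 30/36 = 16.7%.

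**Dependence on the placebo rate.** The protocol gives no 3-month placebo rate, so the rates below are assumptions. Exact power at 29 per group with 80% sufficient on bolus:

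| Assumed placebo rate | Chi-square | Fisher |
|---|---|---|
| 20% | 0.999 | 0.997 |
| 30% | 0.98 | 0.96 |
| 40% | 0.89 | 0.83 |
| 50% | 0.67 | 0.57 |

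Power equals 0.90 at a placebo rate of 39.3% (chi-square) or 36.0% (Fisher). The pooled formula returns 30 (29.4, rounded up) at a placebo rate of 40%. That is a back-calculation and no evidence of what the sponsor assumed.

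**The case against.** The strongest reply is that nothing follows from the error. The protocol describes a pilot in which "the primary objectives of this study are to evaluate the feasibility, the acceptability and the security of the proposed intervention"; the proportion reaching 75 nmol/L is an efficacy question outside those aims. On the stated inputs the trial has more children than it needs, and being about one child per group short of an unsupported 30 does not affect power. This stands, and it is why the point is minor.

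A second reply is that 6% is never called the placebo rate, since raising a proportion to 80% can also be read as a before/after change. Nor is it certain that placebo children will do much better than 6%: the protocol describes supplement use and compliance in this population as low, and only 4 of the 8 users took their supplement at least 4 days a week. The caution is fair. But the paired and one-sample readings give 4 to 14, so the before/after reading does not rescue 30. The trial also plans weekly calls and pill counts to support the daily tablet, so some rise on placebo is plausible. The protocol leaves the size of that rise open, and the placebo rates tabulated above are a sensitivity range, no more.

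Third, the figure of 8 for chi-square comes from the formula, and exact enumeration already reaches 0.907 at 7. That is correct and leaves the conclusion unchanged.

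**Conclusion.** The concern holds, with high confidence and minor severity. The protocol's inputs are complete and lead to 8 to 10 per group with the tests it names, so the stated 30 is at least three times too large for them. Separately, 36 per group with 20% attrition leaves about 29. Both results follow by arithmetic from the protocol's own figures.

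The trial is not underpowered on what it states. Its power would fall below 0.90 only at a placebo rate above roughly 36 to 39%, assuming 80% on bolus and 29 evaluable per group, and nothing in the protocol points to a rate that high. The fault lies in the justification of N; the size of N itself can stand.

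**What to change.** Keep 72 and rewrite the Sample size paragraph:

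- Name the comparison (bolus vs placebo at 3 months, if that is meant) and the test.
- Replace the 6% with an assumed and justified 3-month placebo rate of 25OHD ≥75 nmol/L under 1,000 IU/day, chosen independently of N.
- Report power at about 29 evaluable per group over a range of placebo rates, as in the table above.
- Say that 36 per group with 20% attrition leaves about 29.

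If no placebo rate can be justified, say that N was set on feasibility and give the precision it buys. The largest 95% half-width for a proportion is 1.96 × 0.5/√72 = 0.115 (about 12 points) on all 72 children and 1.96 × 0.5/√36 = 0.163 (about 16 points) on one arm of 36.

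The cost is wording only. The stated power becomes conditional on an assumed placebo rate and may look less favourable.

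### Recruiting 36 per group with 20% attrition leaves 28.8 children per group, not the 30 the protocol says it needs; the figure needs correcting, but power on the stated inputs is not affected

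*Protocol*

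**What the plan says.** The Protocol's sample-size paragraph, under Methodology, starts from the preliminary finding that "only 6% of SCD children had vitamin D sufficiency" and sets a target of 80%. For that increase, "with a power of 0.90" and a two-tailed 5% level, it concludes that "we need 30 patients per group". The next sentence adds the allowance for losses: "Taking into account an attrition rate of 20%, we aim to recruit a total of 72 participants (36 per group").

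The Statistical Analysis section names the "Chi-square test or Fisher's exact test for categorical variables". It does not say which of the two produced the 30.

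The threshold belongs to a secondary objective. Under Research objectives the Protocol lists the change in serum 25OHD as secondary and adds: "At 3 months, a raise of the 25OHD level to 75nmol/L or more is expected". The primary objectives are feasibility, acceptability and safety.

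**The concern.** Attrition is a loss from those recruited, so the allowance should divide the number needed by the fraction expected to remain. The recruited figure instead matches the number needed plus 20% of itself. At the protocol's own attrition rate, the plan therefore does not deliver the number it says it needs.

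The stake is the accuracy of a stated design figure. The paragraph implies that 30 evaluable children per group survive 20% attrition, and that is not so. Attrition is also one of the feasibility outcomes, and the pilot is meant to inform a larger trial. If the same method were carried forward at 20% attrition, that trial would end with 1.20 × 0.80 = 0.96 of its required number, 4% short, and it might not have this pilot's slack in power.

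**Working it through.** **Inputs** (all from the sample-size paragraph unless noted)

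- Reference proportion at or above 75 nmol/L: 6%. Target: 80%.
- Power 0.90, two-sided alpha 0.05.
- Needed per group: 30. Attrition: 20%. Recruited: 36 per group, 72 in total.
- Test: chi-square or Fisher's exact (Statistical Analysis section).

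**Step 1. Reproduce the plan's 36.** The protocol shows no formula. Needed × (1 + attrition) = 30 × 1.20 = 36, which matches exactly. Needed / (1 − attrition) = 30/0.80 = 37.5, so 38 per group or 76 in total, which does not match.

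**Step 2. What 36 per group yields.**

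- At 20% attrition: 36 × 0.80 = 28.8 per group; 72 × 0.80 = 57.6 in total.
- Shortfall against the stated need: 30 − 28.8 = 1.2 per group; 60 − 57.6 = 2.4 in total.
- Largest attrition that still leaves 30: 1 − 30/36 = 16.7%, or 6 of 36.

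**Step 3. Does 30 follow from its inputs?** With p1 = 0.06, p2 = 0.80 and mean 0.43, the pooled-variance formula is

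n = [1.960 × √(2 × 0.43 × 0.57) + 1.282 × √(0.06 × 0.94 + 0.80 × 0.20)]² / 0.74² = (1.968/0.74)² = 7.08, so 8 per group.

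With the continuity correction it is 9.59, so 10. By exact enumeration, power first reaches 0.90 at 7 per group for chi-square (0.907) and at 9 for Fisher (0.905). None of these gives 30.

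**Step 4. Effect on power for 6% against 80%** (exact enumeration).

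| n per group | Chi-square, type II error | Fisher, type II error |
|---|---|---|
| 28 | 8.8 × 10⁻⁷ | 3.4 × 10⁻⁶ |
| 29 | 5.6 × 10⁻⁷ | 2.3 × 10⁻⁶ |

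Power at 28 per group is thus 0.999999 (chi-square) and 0.999997 (Fisher).

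**Step 5. Sensitivity to the control rate.** The protocol gives no control-arm rate other than 6%, so the rates below are assumptions. Exact power against 80%:

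| Control rate (assumed) | Chi-square, n = 29 | Chi-square, n = 30 | Fisher, n = 29 | Fisher, n = 30 |
|---|---|---|---|---|
| 20% | 0.999 | 0.999 | 0.997 | 0.998 |
| 30% | 0.981 | 0.985 | 0.964 | 0.971 |
| 35% | 0.949 | 0.959 | 0.914 | 0.928 |
| 40% | 0.890 | 0.905 | 0.830 | 0.851 |

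The largest loss from 30 to 29 per group is at 40%: 1.5 points for chi-square and 2.1 for Fisher. Rounding 28.8 down to 28 instead, the losses at 40% are 2.2 and 2.8 points. The pooled formula returns 30 per group when the control rate is about 40%. That shows only what would make the 30 fit; it is not a rate the protocol states.

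**The case against.** The strongest reply is that nothing practical turns on this. The gap is 1.2 children per group in a pilot whose primary aims are feasibility, acceptability and safety, and power on the stated inputs is unchanged to five decimals. That stands, and it is why the point is minor.

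A second reply is that the benchmark is itself doubtful. If about 7 to 10 per group suffice, then 28.8 is roughly three times what the stated inputs require, so there is no shortfall against a demonstrated need. That also stands. What remains is an inconsistency between figures that the protocol itself fixes. The unexplained 30 is a separate defect and does not make the attrition error heavier.

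Third, the protocol never prints the number it expects to remain after attrition; 28.8 is derived. This is true, but the sentence has no other purpose than to secure the 30 named just before it.

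Fourth, the conclusion that 72 can stay is shown only for the stated 6% against 80% and, in the assumed cases, for control rates up to 35%. At 40%, power at 29 per group is below 0.90 with either test, and with Fisher it is below 0.90 even at 30. This is a fair limit and is carried into the fix.

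No other passage removes the mismatch. The documents do not define attrition differently or provide for replacing dropouts. Analysing by intention to treat does not supply a missing 3-month 25OHD value.

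**Conclusion.** The concern holds as a minor arithmetic error. Needing 30, losing 20% and recruiting 36 per group cannot all be true: 36 per group gives 28.8 at 20% attrition and gives 30 only if attrition is at most 16.7%. The shortfall is 1.2 per group (2.4 in total). On the stated 6% against 80% it costs no material power, and the primary objectives are untouched. The trial is not shown to be underpowered. The base figure of 30 is also not explained by the inputs printed beside it.

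The attrition result assumes only that attrition means a loss from those recruited without replacement. The statement on power rests on the protocol's 6% and 80%; results at other control rates are illustrations.

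**What to change.** Amend the sample-size paragraph in this order:

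1. State the control-arm proportion and the test that give 30 per group, or replace 30 by the number that the stated inputs give.
2. Restate the attrition sentence, for example: with 36 recruited per group and 20% attrition, about 29 per group are expected to be evaluable; 30 per group would be reached only if attrition is at most 16.7%.
3. Quote the power at about 29 per group for the reconciled control proportion and test.

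The cost is one or two sentences. On the stated inputs recruitment stays at 72 and no extra children are needed. If the reconciled control proportion proves as high as about 40%, the power at 29 per group should be reported as it is, and the target of 0.90 reconsidered against it.

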participation; iv) response rates to questionnaires and compliance to the interventions will be gathered throughout the trial by the research trainee.

2. *Safety*: Urine will be collected by the research nurse at baseline and 3 months and calcium/creatinine ratio measured using automated methods (Clinical Biochemistry Service, Sainte-Justine). At baseline, participants will be provided with a container to collect urine on day 7 (\pm 3days) post-bolus along with the team endocrinologist's prescription for the assessment of urine calcium and creatinine. They will be instructed to bring the urine to the nearest medical clinic for measurement. Results will be communicated to the team endocrinologist for evaluation and management. Serum calcium will be measured if deemed necessary by the endocrinologist. Code breaking will be done only if required for patient management. The proportion of children with episodes of hypercalciuria, hypercalcemia or serum 25OHD levels $>$ 250nmol/L as well as any other adverse health effects will be documented at endpoint while weekly follow-up phone calls will be made by the research trainee to inquire about adverse events.

3. *Dietary intakes and sun exposure*: The research trainee will assess calcium and vitamin D intakes at baseline and endpoint by means of a validated food frequency questionnaire¹⁵. Analysis of the FFQ will be based on values from the Canadian Nutrient File version 2010 and the US Department of Agriculture National Nutrient Database for Standard Reference as done previously¹⁶. Sun exposure will be evaluated with a non-validated questionnaire at both timepoints.

4. *Mean change of 25OHD levels*: To measure this outcome, blood will be collected at baseline and 3 months post bolus by the research nurse. Serum 25OHD will be measured in batches by tandem mass spectrometry at the Clinical Biochemistry Service of Sainte-Justine UHC.

5. *Clinical outcomes*:

Those outcomes will be either collected or measured at baseline and endpoint:

- (i) Growth: weight, height and BMI will be retrieved from medical records.
- (ii) Haematological: complete blood count, lactate dehydrogenase (as index of hemolysis), bilirubin and creatinine. These assessments are routinely performed in these children and will be extracted from medical records.
- (iii) Inflammatory: serum TNF and IL-6 will be measured by ELISA kits in [name] lab.

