- (iv) Bone health and musculoskeletal pain: serum PTH and biochemical markers of bone formation (P1NP) and resorption (C-telopeptides (CTX)) will be measured by standard methods in the Clinical Biochemistry Service, Sainte-Justine or using ELISA kits in [name] lab. Musculoskeletal pain will be assessed with the Brief Pain Inventory (BPI)¹⁷. This questionnaire provides information on the variability of pain intensity as well as on the quality of the pain felt by patients. It takes approximately 10 minutes to complete and will be administered by the research trainee to the participants or their parents (in case of young children).
- (v) SCD-related complications: Other complications affecting bone (e.g. fractures, avascular necrosis, osteomyelitis, bone infarct), the kidneys (e.g. nephrocalcinosis, microalbuminuria), the retina (e.g. retinopathy), blood vessels (e.g. stroke, thrombosis), the heart (cardiomegaly, tachycardia), the lungs

(e.g. asthma, pulmonary hypertension), the spleen (splenomegaly, spleen sequestration crisis), the liver and gallbladder (e.g. hepatomegaly, hepatic cytolysis, cholelithiasis, cholecystitis) will be noted. (vi) Quality of life: Health-related quality of life will be assessed through the Pediatric Quality of life inventory (PedQL). This 23-item validated questionnaire¹⁸ covers four domains: physical, emotional, social and school functioning, takes less than 4 minutes to complete and will be administered by the research trainee separately to the children and their parents.

General characteristics of the participants, such as age, sex, genotype in regards of SCD, ethnicity and drugs taken by the participants will also be collected from medical records.

Data collection will be entirely performed by the research trainee and supervised by the two principal investigators.

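### Serum calcium is a named primary safety measure, but the visible text has it measured only at the endocrinologist's discretion, so the promised hypercalcemia proportion would be incompletely ascertained

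*Protocol*

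**What the plan says.** Under Research Objectives, the third primary objective is the safety of the "bolus (serum and urinary calcium levels, serum 25OHD"). Serum calcium is thus one of three named measures.

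Outcomes, item 2 (Safety) sets out the collection:

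- Urine: "Urine will be collected by the research nurse at baseline and 3 months and calcium/creatinine ratio measured using automated methods". A further urine sample is planned around day 7 after the bolus.
- The handling of the day-7 sample: "Results will be communicated to the team endocrinologist for evaluation and management".
- Directly after that: "Serum calcium will be measured if deemed necessary by the endocrinologist".
- The reported result: "The proportion of children with episodes of hypercalciuria, hypercalcemia or serum 25OHD levels" above 250 nmol/L, documented at endpoint together with other adverse health effects.

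For serum 25OHD, Outcomes, item 4 states that "blood will be collected at baseline and 3 months post bolus by the research nurse". The other blood tests are itemised in Outcomes, item 5: "complete blood count, lactate dehydrogenase (as index of hemolysis), bilirubin and creatinine" under (ii), TNF and IL-6 under (iii), and "serum PTH and biochemical markers of bone formation (P1NP) and resorption" under (iv). Serum calcium is in none of these lists.

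The Statistical Analysis section plans intention-to-treat analysis and between-group comparison of outcomes at baseline and endpoint.

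**The concern.** A rule written for the care of an individual child is the only stated source of data for a primary safety measure. It names no timepoint and no group of children who will all be tested. A proportion with hypercalcemia needs to be known for every child in its denominator, and this rule does not provide that.

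Three consequences follow.

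1. If the denominator is all randomised children, as intention-to-treat suggests, every untested child is counted as unaffected.
2. If the denominator is the tested children, the proportion comes from children picked because something prompted a test.
3. Blinding of the research team means testing should not follow known allocation. Testing may still follow the urine result, however, and if the bolus raises urinary calcium, more children could be tested in the active arm than in the placebo arm.

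The planned comparison of outcomes at baseline and endpoint also cannot be made for serum calcium levels if neither time has a scheduled value. The eligibility criteria exclude only hypercalcemia that is already known, so without a baseline value a later high result in a given child cannot be told apart from a pre-existing one. This matters because the pilot's safety data are intended to inform the design of a larger trial.

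**Working it through.** The protocol gives no figure for this point, so there is none to reproduce. The check sets the three named safety measures side by side and then works out what discretionary testing does to a proportion.

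**Step 1. Scheduled measurements.** The Sample size paragraph gives 72 children (36 per group).

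| Measure in the primary safety objective | Scheduled times in the visible text | Planned measurements |
|---|---|---|
| Urine calcium | baseline, day 7, 3 months | 72 × 3 = 216 |
| Serum 25OHD | baseline, 3 months | 72 × 2 = 144 |
| Serum calcium | none; discretionary only | 0 |

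**Step 2. What the reported proportion estimates.** Let p be the true proportion with hypercalcemia, s the share of those children who are tested while hypercalcemic, and f the share of all children tested. Ignoring false positives:

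- over all randomised children: p × s
- over tested children: p × s / f

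The first equals p only if s = 100%. The second equals p only if s = f, that is, if affected children are no more likely to be tested than others, which is not what a discretionary test is designed to achieve.

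**Step 3. Illustration only.** The protocol gives none of p, s or f; the values below are assumptions that show the direction of the error, not its size. Take p = 10%.

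| s (assumed) | f (assumed) | Over all randomised (p × s) | Over tested (p × s / f) |
|---|---|---|---|
| 50% | 50% | 5% | 10% |
| 50% | 25% | 5% | 20% |
| 50% | 10% | 5% | 50% |
| 100% | 25% | 10% | 40% |

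Over all randomised children the figure can only be too low or correct. Over tested children it is too high whenever s exceeds f. If s or f differs between arms, so does the reported proportion, even with the same p.

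**Step 4. What scheduled testing would allow.** If no child in an arm has a high value, the one-sided 95% upper bound for n children measured is 1 − 0.05^(1/n):

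- n = 36: 1 − 0.05^(1/36) = 8.0%
- n = 30 (the per-group number the protocol plans to have after attrition): 1 − 0.05^(1/30) = 9.5%

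These bounds show what complete measurement at a visit could support. They say nothing about how large the present flaw is.

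**The case against.** The strongest objection concerns the scope of the discretionary sentence. It comes straight after the day-7 urine result is sent to the endocrinologist, and its natural reading is a follow-up to that result. On that reading it is no rule at all for baseline or 3 months, where the text is silent rather than discretionary. This stands as a reading, but it does not rescue the outcome: the objective and the reported proportion still require serum calcium, and no time for it is stated.

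Second, absence from the visible text is not absence from the plan. Fig. 1 (Experimental design) is not shown and could carry a visit schedule. The blood lists are not exhaustive either: fetal hemoglobin is named in the secondary objectives but not itemised under Outcomes. Both points stand. For that reason the finding rests on the discretionary sentence and not on the lists. If Fig. 1 does schedule serum calcium, the Safety paragraph must still be reconciled with it.

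Third, the hypercalcemia wording could be read as a count of documented episodes alongside adverse events, not an estimate from testing everyone. The primary objective, which speaks of calcium levels in serum as well as urine, weighs against this.

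Fourth, the choice of denominator can be left to a statistical analysis plan. That is so, but no analysis plan can supply results from assays that were never run.

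Fifth, assays at baseline and 3 months would leave the early period after the bolus to discretion. This is correct, and the result would have to be worded accordingly.

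Finally, urinary calcium, 25OHD above 250 nmol/L and the weekly adverse-event calls are unaffected and continue to serve the safety objective.

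**Conclusion.** The concern holds, with medium confidence, and should be fixed. One named component of a primary safety objective has no scheduled measurement in the visible text, while the other two are planned for every child. If the protocol is followed as written, the hypercalcemia proportion can be understated over all randomised children, is not representative over those tested, and could differ by arm partly through who was tested.

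No bias size is claimed, since the protocol gives neither the number to be tested nor a hypercalcemia rate. The between-arm concern additionally assumes that the bolus raises urinary calcium and that testing follows the urine result. The conclusion depends on the visible text, with Fig. 1 unseen.

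**What to change.** Reconcile the primary safety objective, Outcomes item 2 and, if it shows a schedule, Fig. 1, in one of two ways.

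**(a) Measure it for outcome purposes.** Assay serum calcium for all children on the baseline and 3-month blood already drawn, if sample volume allows. Report hypercalcemia by arm over the number measured at each visit, and word it as hypercalcemia at those visits, because values in between are not covered. Report discretionary tests separately, by arm, with the number tested. The cost is at most 72 × 2 = 144 assays, or 72 + 60 = 132 if 30 per group reach 3 months; applying the stated 20% attrition to 36 per group gives 28.8 per group and about 130. No extra visit is needed, but sample volume must be confirmed.

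**(b) Reword the outcome.** Remove serum calcium and hypercalcemia from the primary safety outcome and report them descriptively among tested children, with the number tested by arm. This is a change of wording in two places.

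Discretionary testing for patient care is unaffected under either option.
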